# 19.6 Secondary outcome analysis

Secondary endpoints - safety analysis

- proportion of patients requiring study treatment discontinuation
- proportion of patients with serious adverse events (SAEs) during study period (ie treatment period + follow up)

Secondary endpoint - quality of life

• Short-Form Health Survey (SF36) scores at the end of treatment and 3 months post-treatment for both treatment arms. Score range from 0-100, with the highest score representing best quality of life. For each treatment arm, group mean scores at both time points, as well as the change from end of treatment to post-treatment, will be analysed.

To evaluate the tolerability of extended treatment, it is important that any randomised participant who takes at least one dose of the extended phase treatment is included in the analysis.

Comparison of proportions will be analysed by Chi-square test. Comparison of means of continuous variables will be analysed by T-test.

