### 11.6 Trial Design

This is an open-label, parallel design study of 12 and 24 weeks of sofosbuvir/velpatasvir. Subjects are initially started on NHS standard of care treatment, and are consented to participate between treatment week 8-12 (of the standard 12 week course). This design is chosen for several reasons:

- To maximise the time between fulfilling entry criteria (i.e. week 2 ≥ 30iu/mL) and consent, to allow subjects time to consider participation
- Given sofosbuvir/velpatasvir is generally well tolerated, early discontinuation is usually due to non-adherence. By recruiting patients after at least 8 weeks, the study is more likely to recruit subjects willing to adhere to extended treatment. The study specifies that subjects have taken at least 90% of prescribed drugs by screening
- Sofosbuvir/velpatasvir is an expensive treatment and in order to prevent wastage of prescribed NHS treatment when subjects commence on the trial, they are recruited only after the final prescription (each prescription is for one bottle of sofosbuvir/velpatasvir which contains 4 weeks of drug) has been dispensed at treatment week 8. Therefore, only subjects randomised to extended treatment will be dispensed with study drugs.

Maximum duration of participation is 16 weeks for Arm A (12 weeks treatment) - 4 weeks of observation during standard of care treatment, 12 weeks of follow-up, and 28 weeks for Arm B (24 week treatment arm) – 16 weeks of study treatment (4 weeks of standard of care treatment plus 12 weeks of additional IMP treatment), 12 weeks of follow-up.

Treatment week 0 is defined as commencement of sofosbuvir/velpatasvir on NHS treatment programme, before enrolment into the study. Subjects can be pre-screened for study eligibility once week 2 virological response becomes available. Patient information sheet can be provided to interested subjects, but they cannot be consented to participate until week 8 of treatment. Screening and randomisation can take place until the end of standard treatment at week 12.

Upon enrolment into the study until treatment week 12, subjects will proceed according to protocol but they will complete drugs prescribed as part of NHS treatment prior to enrolment. This is in order to reduce wastage of high cost drugs. Sites must ensure sufficient time between enrolment and end of 12 weeks treatment, to dispense additional IMP for participants randomised to arm B (24 weeks).

Study visits are as follows:

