# 17.4 Notification and reporting Adverse Events or Reactions

If the AE is not defined as SERIOUS, the AE is documented in the participant's medical notes and CRF and the participant is followed up by the research team.

Recording of AEs should start from the first day of randomisation, to the post treatment 12 week visit. Since participants have commenced treatment on standard NHS care at the time of enrolment, events which occurred prior to enrolment are retrospectively documented.

Serious adverse events which occur during IMP use (i.e. treatment week 13 to 24) and until end of trial (post-treatment week 12) need to be reported. SAEs occurring during treatment but prior to IMP use need to be recorded in medical notes and CRF, but not reported.

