#### 17.7 Notification and Reporting of Serious Adverse Events & SUSARs

All Serious Adverse Event (SAEs) will be recorded in the participants' notes, the CRF, the sponsor SAE form and reported to the sponsor (Joint Research Management Office) within 24 hours of the PI or co-investigators becoming aware of the event. Nominated co-investigators (as listed will be authorised to sign the SAE forms in the absence of the PI at the participating sites. The sponsor will not consider a SAE 'valid' unless there is written evidence of that the SAE has been medically assessed by the PI or delegated qualified medic (see JRMO SOP 26a - Phamacovigilance reporting for CTIMPs).

Suspected Unexpected Serious Adverse Reactions (SUSARs) that occur during the trial will be reported to the JRMO within 24 hours of the PI or co-investigator becoming aware of the event. SUSARs should be reported to the sponsor (JRMO) within 24 hours. The sponsor will report SUSARs fatal or life-threatening SUSARs as soon as possible, but no later than 7 days after you are first aware of the reaction. Any additional relevant information must be sent within 8 days of the report.

You must report non-fatal or non-life-threatening SUSARs as soon as possible but no later than 15 days after you are first aware of the reaction.

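### The SAE comparison runs up to 28 weeks in Arm B but 16 in Arm A, so it leans against 24 weeks in expectation even if the extension is harmless

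*Protocol*

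**What the plan says.** Section 19.6 of the protocol names two safety endpoints. One is the "proportion of patients with serious adverse events (SAEs) during study period (ie treatment period + follow up"). The other is the "proportion of patients requiring study treatment discontinuation", for which no time window is given. For both, "Comparison of proportions will be analysed by Chi-square test". Section 19.3 presents these analyses as set in advance, so the protocol itself fixes the endpoint and the test.

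The length of the study period depends on the arm. Section 11.6 states: "Maximum duration of participation is 16 weeks for Arm A (12 weeks treatment"), which it splits into 4 weeks observed while standard treatment is completed and 12 weeks afterwards. For the other arm it gives "28 weeks for Arm B (24 week treatment arm) – 16 weeks of study treatment" and then the same 12 weeks afterwards. The visit lists in 11.6 agree: Arm A ends at treatment week 24 and Arm B at week 36. Section 17.4 records adverse events from randomisation to the visit 12 weeks after treatment, which again falls 12 weeks later in Arm B.

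No common window, person-time rate or time-to-event comparison is stated.

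**The concern.** A comparison of crude proportions isolates the effect of treatment only if both arms are watched for the same time. Here Arm B is watched for 12 weeks more, in patients who will have serious events whatever drug they take. Section 12.1 admits decompensated cirrhosis, hepatocellular carcinoma and liver transplant. Section 17.5 says that ascites, encephalopathy and variceal bleeding are to be expected from the disease being treated; when serious, these count towards the endpoint.

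The safety contrast matters to the trial's question. Section 9.1 (Proposed study) and Section 9.2 ask whether any gain in cure justifies added side effects, and Section 15.2 says that NHS England would adopt the 24-week regimen if the evidence supports it. An excess of SAEs in Arm B that came only from longer observation could be taken as toxicity.

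**Working it through.** **Inputs from the protocol.** Arm A: 4 weeks on treatment + 12 weeks of follow-up = 16 weeks. Arm B: 4 + 12 weeks on treatment + 12 weeks of follow-up = 28 weeks (11.6). Planned 30 patients per arm (19.1). The stated totals reproduce. Their ratio is 28/16 = 1.75 and their difference 12 weeks.

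**Assumptions, not in the protocol.** A share r of patients has an SAE within 16 weeks, with r = 5%, 10% or 20%. The hazard is constant and the same in both arms, so the extension is harmless.

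**Formula.** Weekly hazard λ = −ln(1 − r)/16. Proportion with an SAE by w weeks = 1 − exp(−λw). For r = 10%: λ = 0.10536/16 = 0.00659, and 1 − exp(−0.00659 × 28) = 1 − exp(−0.1844) = 16.8%.

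The last two columns give the probability that an uncorrected chi-square test at two-sided 0.05 is significant with Arm B higher, by exact enumeration of all outcomes with 30 per arm.

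| r (16 weeks) | λ per week | Arm A, 16 wk | Arm B, 28 wk | Ratio | False Arm B excess, 16 v 28 wk | Same, 16 wk in both arms |
|---|---|---|---|---|---|---|
| 5% | 0.00321 | 5.0% | 8.6% | 1.72 | 6.9% | 1.4% |
| 10% | 0.00659 | 10.0% | 16.8% | 1.68 | 12.2% | 2.7% |
| 20% | 0.01395 | 20.0% | 32.3% | 1.62 | 18.8% | 2.4% |

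**Other readings of the window, at r = 10%.** The figures 16 and 28 are maxima for entry at week 8.
- Randomised at week 12 (12 v 24 weeks): 7.6% v 14.6%.
- End-of-study visit at the limit of its +28 days (20 v 32 weeks): 12.3% v 19.0%.
- Counted from treatment week 0, since 17.4 also documents earlier events (24 v 36 weeks): 14.6% v 21.1%.

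The gap is 12 weeks and the direction the same each time.

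**Discontinuation.** Nobody can stop treatment during follow-up, so 16 v 28 weeks is not the time at risk. After enrolment at week 8 it is about 4 weeks in Arm A and 16 in Arm B. At an assumed 10% per 16 weeks: 1 − 0.90^(4/16) = 2.6% v 10.0%. Counted from week 0 (12 v 24 weeks): 7.6% v 14.6%.

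**After the change.** With one window in both arms, the expected SAE proportions are equal under a harmless extension. First-SAE rates per patient-week also have an expected ratio of 1.0 under the constant hazard.

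**The case against.** The strongest objection is that the whole-course proportion is a legitimate quantity. A longer course entails a longer period in which things can go wrong, and Section 11.2 aims to assess the safety and tolerability of each duration. This stands: the proportion describes the burden of each strategy. It does not tell drug toxicity apart from observation time, and nothing in 19.6 warns the reader of that. The same applies to discontinuation, since more opportunity to stop is part of a longer regimen.

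It can also be said that the background rates are invented, that the constant hazard is a convenience, and that this is a secondary endpoint without a decision rule. All true. The size is illustrative; the direction needs only that some SAEs arise from the disease. Section 9.2 cites a direct comparison of the two durations in advanced cirrhosis without a significant increase in adverse events. That may reassure about the drug, but it does not change what this trial's comparison measures.

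Three stronger readings are tempting and are not supported.
- A reader might infer that SAEs are captured differently by arm. Section 17.4 says "SAEs occurring during treatment but prior to IMP use need to be recorded in medical notes and CRF, but not reported", while 17.7 says "All Serious Adverse Event (SAEs) will be recorded in the participants' notes, the CRF, the sponsor SAE form and reported to the sponsor". The two conflict on notification to the sponsor. But 17.4 still puts earlier SAEs in the CRF, recording runs from randomisation in both arms, and the schedules in 13.8.2 record events at each visit in both. Unequal endpoint capture is not shown.
- A reader might infer that the trial will find 24 weeks less safe. In most repetitions with 30 per arm, the false excess would not reach significance.
- A reader might think that an exact test is the remedy for rare events. Changing the test does nothing about unequal time.

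**Conclusion.** The point holds for the SAE comparison. By the protocol's own figures Arm B is observed 12 weeks longer, and the crude proportions are therefore biased in expectation against 24 weeks. Under the assumed 5% to 20% per 16 weeks and a constant hazard common to both arms, a harmless extension would show about 1.6 to 1.7 times the SAE proportion of Arm A. The chance of a falsely significant excess rises from about 1% to 3% with equal windows to about 7% to 19%.

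Discontinuation has a relatively larger imbalance in time at risk, about 4 against 16 weeks after enrolment. It remains a fair description of how many complete each course, but the between-arm test should not be read as a difference in tolerability.

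The change is worth making because the bias is predictable, runs in one direction and can be removed with data already collected. It does not touch the primary endpoint.

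**What to change.** In Section 19.6:
- Make the between-arm SAE comparison over a common window, from randomisation to the treatment week 24 date. Apply this as a date cut in both arms, because the week 24 visit has a window of +28 days in Arm A and ±7 days in Arm B (13.8.2).
- Report whole-period SAEs as exposure-adjusted patient incidence: patients with a first SAE divided by patient-weeks at risk, by arm. Counting patients rather than events keeps one repeatedly admitted patient from dominating.
- Keep whole-course proportions, labelled as a description of each strategy's burden.
- Report discontinuation of the extension (weeks 13 to 24) descriptively for Arm B, and state that the crude between-arm test is not a measure of tolerability.

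Separately, reconcile the wording of 17.4 and 17.7 on which SAEs are notified to the sponsor.

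The cost is a few sentences. Both arms have visits at weeks 12, 16, 20 and 24, and SAEs are recorded at each, so no new data are needed. The small downside is that the tested window leaves out Arm B's post-treatment weeks 24 to 36. Events then appear only in the whole-period rates and the descriptive proportions.

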## 11.2 Secondary Objective/s

To assess the safety and tolerability of sofosbuvir/velpatasvir for 12 and 24 weeks.

To assess patient reported outcomes (defined as SF36 scores at the end of therapy) in patients receiving 12 or 24 weeks of sofosbuvir/velpatasvir

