## 11.3.2 Secondary Endpoint

- Proportion of patients requiring study treatment discontinuation
- Proportion of patients with serious adverse events (SAEs) during the study period. SAE is
  defined as a medical event which results in death, is life-threatening, requires hospitalisation
  or prolongation of existing hospitalisation, results in persistent or significant disability or
  incapacity, or is a congenital anomaly or birth defect
- Quality of life assessed by SF36 questionnaires at the end of study treatment and at the end of study follow up (3 months post-treatment)

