# 11.5 Objectives and End Points Summary

Primary Objective	Primary Endpoint	Outcome Measures		
Compare efficacy between 12 and 24 weeks treatment (sofosbuvir/velpatasvir) in patients with genotype 3 HCV and cirrhosis who have detectable virus after 2 weeks therapy	SVR12 defined as HCV RNA below limit of quantification up to 15 iu/mL - 12 weeks (up to 16 weeks) after treatment discontinuation	
 
Proportion of patients in 12 week arm achieving SVR12
 
Proportion of patients in 24 week arm achieving SVR24
 
		
Secondary Objective	Secondary Endpoints	Outcome Measures		
	
 
Study treatment discontinuation
 
Serious adverse events
 
Quality of life questionnaire at treatment end
 
Quality of life questionnaire at 3 months post-treatment
 
	Proportion of patients in 12 and 24 week arm developing any of listed secondary endpoints  Quality of life score at the end of treatment and at 3 months post treatment, and change in scores over 3 months, for patients in 12 and 24 week treatment arm		

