#### Study assessments

Once enrolled (treatment weeks 8 up to 12), participants will be randomised. Randomisation must occur before the last dose of treatment at week 12 so that participants in the 24 week arm will be supplied with adequate study drugs. Study sites must ensure there is sufficient time to arrange dispensing of additional study drug so that treatment is not interrupted.

After the participant is enrolled they will carry a patient card to identify them as part of the study.

Visits outside of the study schedule are permitted - relevant data will be captured at the next study visit as per protocol.

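### SF-36 is first collected after randomisation, so the planned change score could hide or reverse an Arm B deficit if compared between arms, and the sound end-of-therapy comparison has no baseline to adjust for.

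*Protocol*

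**What the plan says.** The secondary objective in section 11.2 reads "To assess patient reported outcomes (defined as SF36 scores at the end of therapy", for patients on 12 or 24 weeks. Section 11.3.2 lists the endpoint as "Quality of life assessed by SF36 questionnaires at the end of study treatment and at the end of study follow up". The summary table in section 11.5 adds the "and change in scores over 3 months" to the scores themselves.

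Section 19.6 gives the analysis. On the scale it says "Score range from 0-100, with the highest score representing best quality of life". For each arm, "group mean scores at both time points, as well as the change from end of treatment to post-treatment, will be analysed". On testing it says "Comparison of means of continuous variables will be analysed by T-test".

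The schedules in section 13.8.2 and the visit text in section 13.8.3 agree on timing. Arm A completes SF-36 at week 12 (end of treatment) and week 24 (end of study). Arm B completes it at week 24 (end of treatment) and week 36 (end of study). Neither the screening procedures in section 13.4 nor the screening/baseline visit in section 13.8.3 includes it. On allocation, section 13.8.3 says "Once enrolled (treatment weeks 8 up to 12), participants will be randomised", and this must happen before the last week-12 dose.

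**The concern.** A change score is usually read against a starting value that treatment could not have affected. Here the starting value comes after allocation and at the end of drug exposure: 12 weeks of drug in Arm A, 24 in Arm B. If the extra 12 weeks lower quality of life, the loss is built into Arm B's starting value. Recovery afterwards then looks like improvement, and lasting harm disappears.

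Section 9.2 treats it as an open question whether added side effects of extension are justified, and section 15.2 says that NHS England would adopt the regimen if the trial supports it. A quality-of-life summary pointing the wrong way would bear on that decision. A later analysis plan can choose a model, but it cannot supply a baseline score that was never collected.

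**Working it through.** **The plan's own figure.** The protocol gives no sample-size figure for SF-36. Its only one is 24 per arm for SVR12 (section 19.1: 65% against 95%, 80% power, 95% confidence). The unpooled formula reproduces it: (1.96 + 0.842)² × (0.65 × 0.35 + 0.95 × 0.05) / 0.30² = 23.98, rounded up to 24. Nothing below depends on it. The planned 30 per arm is used.

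**Timing.**

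| | Arm A | Arm B |
|---|---|---|
| Randomisation | weeks 8–12 | weeks 8–12 |
| First SF-36 (end of treatment) | week 12 | week 24 |
| Second SF-36 (3 months after treatment) | week 24 | week 36 |

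No score precedes allocation, and the change starts 12 weeks later in Arm B.

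**What the change score does.** Assume for illustration that both arms average 50 before randomisation, that Arm A stays at 50 at end of treatment and reaches 55 three months later, and that Arm B is d points lower at end of treatment.

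- *Deficit resolves (Arm B also reaches 55).* Change in A = 55 − 50 = 5. Change in B = 55 − (50 − d) = 5 + d. B minus A = +d, that is +2, +5 or +10 for d = 2, 5 or 10, although final scores are equal. Measured from a pre-randomisation score, B minus A would be −d at end of treatment and 0 at 3 months.
- *Deficit persists (Arm B reaches 55 − d).* Change in B = (55 − d) − (50 − d) = 5. B minus A = 0.

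**How often the reversal would reach significance.** The protocol gives no SF-36 SD or correlation. Assume d = 5 with full recovery, SD 10 to 20, and a correlation r of 0.5 to 0.7 between the two scores. The SD of the change is SD × √(2(1 − r)): 10.0 to 7.7 for SD 10, and 20.0 to 15.5 for SD 20. With 30 per arm and two-sided 5%, a t-test on change would favour Arm B significantly with probability 49% to 71% (SD 10) or 16% to 24% (SD 20).

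**Precision of the end-of-therapy comparison.** With 30 per arm, two-sided 5% and 80% power, the two-sample t-test detects 0.736 SD. Adjusting for a baseline score with correlation r to the outcome multiplies this by √(1 − r²):

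| r (assumed) | Detectable difference | Equivalent sample-size factor, 1/(1 − r²) |
|---|---|---|
| no adjustment | 0.736 SD | 1 |
| 0.5 | 0.736 × 0.866 = 0.637 SD | 1.33 |
| 0.6 | 0.736 × 0.800 = 0.589 SD | 1.56 |
| 0.7 | 0.736 × 0.714 = 0.526 SD | 1.96 |

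For a 5-point deficit, power is 49% unadjusted and 61% to 77% adjusted at SD 10, and 16% unadjusted and 20% to 27% adjusted at SD 20. The percentages here and in the previous step use a normal approximation; exact t-test values are up to about 1.5 points lower.

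**The case against.** The strongest reply is that the stated objective is the end-of-therapy score, not the change. Section 19.6 analyses the means at both time points as well, so a worse Arm B score at end of treatment would be seen directly and with the right sign, beside the change that obscures it. This stands. A reader might infer that the trial's whole quality-of-life conclusion could have the wrong sign; the documents do not support that.

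A reader might also infer that, without a baseline, the end-of-therapy comparison cannot tell a treatment effect from chance imbalance. That is not so. Allocation is randomised and stratified by decompensation (section 13.5.1), and the t-test's standard error already allows for chance imbalance. What is lost is precision.

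Next, section 19.6 can be read as reporting change within each arm only, which would be harmless. That reading is possible but not secured: the t-test sentence in the same section covers continuous means without excluding change, and section 11.5 lists change as an outcome measure for both arms.

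Finally, reversal needs a real Arm B deficit that recovers within 3 months, and sections 9.2 and 15.2 cite no increase in adverse events at 24 weeks. This limits how likely the problem is. It does not make the change score informative about harm: a resolving deficit reverses and a lasting one vanishes.

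**Conclusion.** The point holds in limited form. The schedule contains no pre-randomisation SF-36, and the planned change starts from a post-randomisation, on-treatment value. If that change is tested between arms, a resolving Arm B deficit of d points appears as a d-point advantage and a persistent one cancels. The end-of-therapy comparison remains valid; its weakness is that it detects only about 0.74 SD where 0.64 to 0.53 SD would be possible. The sign argument is arithmetic. The significance probabilities and precision gain rest on assumed SDs of 10 to 20 and correlations of 0.5 to 0.7, which the protocol does not give. This is a secondary endpoint in a trial sized on SVR12, so low power for SF-36 is not itself an error and the primary conclusion is untouched. The change is worth making because it is cheap and cannot be made after the fact.

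**What to change.** Add SF-36 to the screening/baseline visit at weeks 8 to 12, completed before randomisation. Patients are on treatment by then, but both arms are on the same regimen and allocation is not yet known, so the score is a valid covariate.

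In section 19.6, compare arms at end of treatment and at 3 months post-treatment by ANCOVA on that score. State that the change from end of treatment to post-treatment is described within arm and not tested between arms, and align section 11.5.

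A comparison at week 24, when both arms already complete SF-36, could be added as supplementary. It should not replace the section 11.2 comparison: it sets Arm A patients off drug against Arm B patients finishing drug, and the visit windows differ (+28 days in Arm A, ±7 days in Arm B, so visits could be up to 28 + 7 = 35 days apart). Both limits should be stated.

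The cost is one more paper form at an existing visit, a schedule edit and an amendment. Participants already randomised will have no baseline score, so the gain shrinks with delay.
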